
KEY PERSONNEL (List names of all investigators including PI and their respective specialties)

Name	Professional Discipline/ Specialty	Role in the Project
1. [name]	Environmental Microbiologist	PI
2. [name]	Sustainable Development Specialist	Co-PI
3. [name]	Environmental Health Specialist	Co- PI
4. [name]	Epidemiologist	Co-I
5. [name]	Microbiologist	Co-I

DESCRIPTION OF THE RESEARCH PROJECT

Hypothesis to be tested:

Concisely list in order, in the space provided, the hypothesis to be tested and the Specific Aims of the proposed study. Provide the scientific basis of the hypothesis, critically examining the observations leading to the formulation of the hypothesis.

We postulate that the ecology of *Vibrio cholerae* O1 in Mozambique will be similar to Bangladesh and similar environmental intervention may be applicable to reduce the incidence of cholera in Mozambique.

Specific Aims:

Describe the specific aims of the proposed study. State the specific parameters, biological functions/ rates/ processes that will be assessed by specific methods (TYPE WITHIN LIMITS).

- 1) Transfer of technology from ICDDR,B laboratories in Bangladesh to the Center for Environmental Hygiene and Medical Exams (CHAEM) at Beira of Mozambique.
- 2) To find out the role of phytoplankton and zooplankton as habitat of *V. cholerae* in the aquatic environment of Mozambique
- 3) To see the role of various physicochemical parameters in multiplication of *V. cholerae* O1 in the aquatic environment of Bangladesh and Mozambique.
- 4) To find out intervention strategies to reduce cholera incidence at Beira, Mozambique.

Background of the Project including Preliminary Observations

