In epidemiological and ecological study in Bangladesh for the last 5 years, it has been observed that phytoplankton and zooplankton can act as microhabitat for *V. cholerae* O1 in the aquatic environment of Bangladesh (Table. 1). We do not know whether similar situation exists in Mozambique.

[figure not shown]

Fig. 6. Relationship between incidence of cholera and rainfall in Mozambique

[figure not shown]

Fig. 7. Seasonal dynamics of pH and water temperature in a fresh water lake in Bangladesh, compared rainfall and the number of cholera cases in the surrounding area. Note that the peak in cholera cases follows the peak in rainfall and coincides with a temperature peak.

Table 1: Isolation of culturable *V. cholerae* O1 from the various components of aquatic environments of Bangladesh during 1999 to 2002

Components	Total number of samples	Total number of isolates
Water	1923	21
Zooplankton	1923	12
Phytoplankton	1923	12
Water Hyacinth	758	2

It has been observed that the seasonality of cholera in Bangladesh is also associated with the seasonality of plankton bloom formation in the aquatic environment of Bangladesh (Islam *et al.*, 1994b). The multiplication of the phytoplankton and zooplankton in the aquatic environment is also related with the changes of various physicochemical parameters of water (Islam *et al.*, 1994b). As phytoplankton is the food for zooplankton, the phytoplankton bloom is followed by the zooplankton bloom. It is not known whether similar changes of the physicochemical parameters of water in the cholera endemic areas of Mozambique also take place during cholera seasons, Therefore in the present study a comparison of all these factors will be considered.

Studies have also shown that the toxigenic *V. cholerae* during association with the aquatic plants do not lose their pathogenic properties (Islam *et al.*, 1990a, 1990b, 1993b) but after certain times become nonculturable (Colwell and Huq, 1994; Colwell *et al.*, 1996; Islam *et al.*, 1990a, 1994b; Huq *et al.*, 1990). These viable and noncultureable *V. cholerae* have been detected both in association with the blue green algae and zooplankton from the aquatic environment in Bangladesh (Islam *et al.*, 1994b; Huq *et al.*, 1990). Therefore attempts will be made to see whether *V. cholerae* also remains in association with the plankton in the aquatic environment of Mozambique in viable but noncultureable (VBNC) form.

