The sampling at Beira, Mozambique for the analysis of cholera ecology will include the sea, river, well water, and other surface water bodies. Basic water chemistry tests at sites will include conductivity, pH, temperature, salinity, dissolved oxygen and total dissolved solids. In the laboratory we will analyze free carbon dioxide, chlorides and hardness. Tests for *V. cholerae* will include culture by enrichment technique to (qualitative) assess the presence of vibrios in water, phytoplankton and zooplankton. Faecal coliforms in water will be counted by the membrane filtration technique; fluorescent microscopy will indicate the non-culturable vibrios, alive or dead. Colony blots will provide the detailed quantitative assessment of vibrios in the sample. All of these tests will be carried out every 15-day interval throughout the study. The CHAEM laboratory at Beira has been selected as the main base for developing capacity and for carrying out some of the microbiological analysis for this research. Procedures will be set up as part of the future monitoring system. In course of time, the more routine laboratory procedures will also eventually be enhanced at Quelimane and Maputo. Equipment for chemical and microbiological testing used in this research will remain with the centre at Beira after completion of the project.

Phase II: Like Bangladesh, if it is found in the first phase of the study that phytoplankton and zooplankton are also acting as reservoirs of cholera in Mozambique, then environmental cholera intervention strategy will be introduced using capulanas as a filtering device in the second phase. The intervention study will be carried out in two phases. The first phase study will be in-depth laboratory-based investigation to find out the effectiveness of capulanas to remove phytoplankton and zooplankton associated *V. cholerae* O1 and O139. In the second phase, acceptability and effectiveness of capulanas will be investigated in the community to reduce cholera incidence.

After successful completion of the first phase, which includes the identification of risk factors of cholera and its environmental intervention, attempts will be made in the second phase to focus on the identification of the risk factors for other infectious diseases in Mozambique particularly for Shigellosis.

Environmental monitoring

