The preserved samples will be shaken gently for proper mixing from which 1ml sub- samples will be drawn by pipette and transferred into a Sedgewick-Rafter (S-R) counting cell following standard procedure (APHA, 1998). The samples will then be placed under a compound binocular microscope at a magnification of 10X and then observed for identification and enumeration. The magnification of the compound microscope are sometimes adjusted to 4X, 40X or 100X according to the need for better observation and identification. The zooplanktons are identified by using the taxonomic keys, identifying characteristics and specific figures following Ward & Whipple (1959), APHA (1998), Needham & Needham (1961), Bhouyain & Asmat (1992) and other relevant literatures.

After identification of zooplankton in each sample, they will then be enumerated for their abundance. At least a total of 100 strips (sub-cells) of S-R cell will randomly examined for each sample and the zooplankton lying within that area will be counted for each species, genera, group and phylum wise. The total numbers of zooplankton will be estimated following the formula described above for phytoplankton.

Water

One liter water sample will be collected from each sampling site in a one liter capacity Nalgene (Nalgene company, USA) plastic bottle. This water will be collected after passing through a 20-µm mesh size Millipore plankton net to make water free from zooplankton and phytoplankton. This water will be used for both microbiological and chemical analyses.

Culture of *V. cholerae* from zooplankton, phytoplankton and water

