All the environmental samples will be processed in the Environmental Microbiology Laboratory in Dhaka. All the techniques required for testing the environmental samples are already in place in this laboratory with adequate manpower and expertise. All the equipments are also available in this laboratory.

Data Analysis

Describe plans for data analysis. Indicate whether data will be analyzed by the investigators themselves or by other professionals. Specify what statistical software packages will be used and if the study is blinded, when the code will be opened. For clinical trials, indicate if interim data analysis will be required to monitor further progress of the study. (TYPE WITHIN THE PROVIDED SPACE).

The isolation and enumeration of *V. cholerae* O1 and O139 from various environmental samples by culture, FA, and colony blot hybridization will be related with the physicochemical parameters of water and the seasonality of cholera. The data from Bangladesh will be compared with the data from Mozambique to find out the role of environmental factors in the seasonality and endemicity of cholera in these two countries.

Logistic regression analysis will be done to do the qualitative analysis (i.e., the presence and absence of *V. cholerae* O1 and O139 using culture technique). For quantitative analysis, Poisson regression analysis will be used.

The biweekly data from both the lotic and lentic environment will be analyzed by first computing the percentage of samples positive by FA, conventional culture and colony blot hybridization by site combination using McNemar test (Sokal and Rohlf, 1989).

A two-way analysis of variance will be performed with site and month as the effects in the model and model assumptions will be determined by examining residuals for normality following the procedures described by Sokal and Rohlf (1989).

The correlation of association between phytoplankton and zooplankton with *V. cholerae* will be analyzed using Pearson's correlation method.

Ethical Assurance for Protection of Human Rights

Describe in the space provided the justifications for conducting this research in human subjects. If the study needs observations on sick individuals, provide sufficient reasons for using them. Indicate how subject's rights are protected and if there is any benefit or risk to each subject of the study.

No human subject is involved in this environmental study.

Use of Animals

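### Pearson's correlation, with no transformation stated, is the only analysis that names plankton; it fits bloom-type counts and presence/absence data poorly and can lose much of its power when blooms are large

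*Protocol*

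**What the plan says.** Aim 2 (Specific Aims) is "To find out the role of phytoplankton and zooplankton as habitat of" *V. cholerae* in Mozambique.

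The Data Analysis section has one sentence that names plankton. It begins "The correlation of association between phytoplankton and zooplankton with" *V. cholerae*, and says that this "will be analyzed using Pearson's correlation method". It does not state a scale or transformation, or which *V. cholerae* measure enters (culture, fluorescent antibody or colony blot).

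The same section assigns regressions by type of result: "Logistic regression analysis will be done to do the qualitative analysis" and "For quantitative analysis, Poisson regression analysis will be used". Neither sentence names a predictor. The general sentence that opens the section relates the *V. cholerae* results to water chemistry and cholera season, not to plankton abundance.

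On the data themselves:
- The Background reports that "the seasonality of cholera in Bangladesh is also associated with the seasonality of plankton bloom formation".
- Methods plans "culture by enrichment technique to (qualitative) assess the presence of vibrios in water, phytoplankton and zooplankton", and adds that colony blots will supply the quantitative assessment.
- Under Zooplankton, "the zooplankton lying within that area will be counted for each species, genera, group and phylum wise"; phytoplankton is likewise enumerated. Plankton densities will therefore be available for every sample.

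**The concern.** Pearson's coefficient measures straight-line association on the scale it is given. Organisms that bloom usually have densities with a long right tail. On the untransformed scale one or two bloom samples can then decide the coefficient, and the many ordinary samples contribute little. A steady association on the log scale can shrink to almost nothing on the raw scale.

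The method also fits the other half of the data poorly. For presence/absence results the protocol has already chosen logistic regression, but the plankton sentence does not use it. The two-way ANOVA gets a residual check for normality; the Pearson sentence gets no comparable check.

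At stake is the sensitivity of the one named analysis that links plankton abundance to *V. cholerae*. A true association could be reported as weak or absent because of the scale used. Correcting for season or serial dependence would not cure this, because the loss comes from the scale.

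**Working it through.** **1. Sample size (Environmental monitoring).** 26 samples a year × 2 Matlab water systems × 3 years = 156 of each type, and 156 × 3 types = 468. The protocol's figures reproduce. Per site, 26 × 3 = 78. The number of Beira sites is not given, so 78 and 156 stand in for it. No alpha, power or target correlation is stated for the plankton question; two-sided 5% is assumed.

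**2. What skew does to the coefficient.** Assume both measures are log-normal with the same log10 SD *d* and log-scale correlation ρ. With s² = (d × ln 10)², the population correlation of the raw values is

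r_raw = (exp(ρs²) − 1) / (exp(s²) − 1).

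For ρ = 0.4:

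| log10 SD | s² | r_raw |
|---|---|---|
| 0.3 | 0.477 | 0.34 |
| 0.5 | 1.325 | 0.25 |
| 0.75 | 2.982 | 0.12 |
| 1.0 | 5.302 | 0.04 |

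**3. Power with counts on both sides** (simulation, independent samples; spread and ρ are assumptions):

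| n, ρ | Method | SD 0.3 | SD 0.5 | SD 0.75 | SD 1.0 |
|---|---|---|---|---|---|
| 78, 0.4 | Pearson, raw | 84% | 62% | 41% | 31% |
| 78, 0.4 | Pearson, logs | 96% | 96% | 96% | 96% |
| 78, 0.4 | Spearman | 94% | 94% | 94% | 94% |
| 156, 0.3 | Pearson, raw | 86% | 61% | 34% | 24% |
| 156, 0.3 | Pearson, logs | 97% | 97% | 97% | 97% |
| 156, 0.3 | Spearman | 95% | 95% | 95% | 95% |

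Log-scale Pearson and Spearman do not depend on the spread, so one figure serves each row. With ρ = 0 all three methods reject in about 4% to 6% of runs, so the comparison is not bought with false positives.

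**4. Power with presence/absence on the *V. cholerae* side** (n = 156; assumed odds ratio 2 per SD of log plankton; raw Pearson at log10 SD 0.3, 0.5, 0.75 and 1.0):

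| Positivity | Pearson, raw | Logistic on log plankton |
|---|---|---|
| 0.62% | 12, 11, 9, 8% | 9% |
| 1.1% | 18, 17, 14, 12% | 14% |
| 5% | 46, 42, 37, 33% | 44% |
| 12% | 73, 64, 54, 48% | 76% |
| 30% | 93, 85, 71, 57% | 96% |
| 50% | 95, 87, 65, 44% | 98% |

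The first row is the rate for zooplankton and for phytoplankton in Table 1 of the Background, 12/1923 = 0.62%. The second is close to that table's water rate, 21/1923 = 1.1%. The 12% is the O139 rate in water that the Background cites. The others are assumed.

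**5. Why the top rows are low for both methods.** At 12/1923, 156 samples give 156 × 0.00624 = 0.97 expected positives. The chance of none is (1 − 0.00624)^156 = 38%, and of at most two, 93%. No choice of test recovers an association from about one positive.

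**The case against.** **The protocol does not say the values are raw.** That is true. Untransformed values are the natural reading of a sentence that names Pearson and nothing else, but it is a reading. A transformation could be fixed in a statistical analysis plan that is not shown. What stands against this is that the protocol commits to a named method, so the point concerns a stated choice, not an absent detail.

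**The *V. cholerae* data are not only presence/absence, and regressions are already planned.** Also true: colony blots give counts, and logistic and Poisson regression cover results from all sample types. The gap is narrower than a missing analysis. Plankton abundance is not named as a predictor in either regression.

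**Stronger readings that the documents do not support:**
- *Pearson would miss a real link most of the time.* Even under the assumptions above, raw Pearson keeps 84% and 62% power at the two smaller spreads. The majority miss needs a wide spread, and the protocol gives no plankton SD.
- *A rare binary result caps the coefficient at about 0.22, near the 5% critical value for n = 78.* That ceiling holds for a normally distributed predictor, that is, for plankton on the log scale. For a log-normal predictor at 12/1923 under perfect threshold dependence the ceiling is 0.47, 0.63, 0.63 and 0.37 at log10 SDs of 0.3, 0.5, 0.75 and 1.0, well above the critical value.
- *A null correlation would decide Phase II.* The Background recognises a reservoir when *V. cholerae* is found together with blue-green algae and copepods in a water source. That is direct detection, and no passage makes a significant correlation the criterion.

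**Conclusion.** The point holds as a matter of method choice. The one analysis sentence that names plankton specifies a method poorly matched to bloom-type densities and to count or binary *V. cholerae* results, and better-matched methods cost nothing.

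The size depends on the spread. With counts on both sides, n = 78 and log-scale correlation 0.4, the loss against log-scale Pearson is about 12 percentage points at log10 SD 0.3 (96 − 84) and about 65 at log10 SD 1.0 (96 − 31). With presence/absence at 12% positivity and odds ratio 2 (n = 156), it runs from 3 points (76 − 73) to 28 (76 − 48). At the protocol's own O1 culture rates it disappears, because too few positives are expected for any method.

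These figures rest on assumed log-normal shape, spread, effect size and alpha, on independent samples, and on Matlab's numbers. Serial correlation and shared seasonality were not modelled, and the number of Beira sites, where Aim 2 applies, is not stated. This should be changed, but it does not put the study's conclusions at risk by itself.

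**What to change.** Replace the Pearson sentence in Data Analysis by:

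> Association of plankton density with *V. cholerae* counts: Spearman's rank correlation (or Pearson's correlation on log10(count+1)). Association with presence/absence: the planned logistic regression, with log10 plankton density as predictor.

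The choice between Spearman and log-scale Pearson should be made before the data are seen. The cost is one sentence: no new samples or measurements are needed, since plankton is already enumerated and logistic regression is already planned. The change does not remedy the small number of O1 culture positives expected in plankton. There, results should be reported as sparse, whichever method is used.

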Principal Investigator: [name]. [name]

Division: LSD

[contact], [name]

Address: Environmental Microbiology Lab. LSD, ICDDR,B

Email: [contact]

Co-Principal Investigator(s): [name], University of Northumbria, UK.
[name], Maputo, Mozambique

Co-Investigator(s): [name], ICDDR, B
[name], ICDDR, B

Student Investigator/Intern: N/A

Collaborating Institute(s): University of Northumbria, UK.
Ministry of Health, Mozambique

Population: Inclusion of special groups (Check all that apply): Not Applicable

- Gender Male Females Age 0 - 5 years 5 - 9 years 10 - 19 years 20 - 64 years 65 +
- Pregnant Women Fetuses Prisoners Destitutes Service providers Cognitively Impaired CSW Others (specify _____) Animal

Project / study Site (Check all the apply):

- Dhaka Hospital Matlab Hospital Matlab DSS area Matlab non-DSS area Mirzapur Dhaka Community Chakaria Abhoynagar
- Mirsarai Patyia Other areas in Bangladesh _____ Outside Bangladesh name of country: Mozambique Multi centre trial (Name other countries involved)

Type of Study (Check all that apply):

- Case Control study Community based trial / intervention Program Project (Umbrella) Secondary Data Analysis Clinical Trial (Hospital/Clinic) Family follow-up study
- Cross sectional survey Longitudinal Study (cohort or follow-up) Record Review Prophylactic trial Surveillance / monitoring Others

Targeted Population (Check all that apply): Not Applicable

- No ethnic selection (Bangladeshi) Bangalee Tribal groups Expatriates Immigrants Refugee

Consent Process (Check all that apply): Not Applicable

- Written Oral None Bengali language English language

Proposed Sample size: Not Applicable

Sub-group _____ Total sample size: _____

Determination of Risk: Does the Research Involve (Check all that apply): Not Applicable

- Human exposure to radioactive agents? Fetal tissue or abortus? Investigational new device? (specify _____) Existing data available from Co-investigator Human exposure to infectious agents? Investigational new drug Existing data available via public archives/source Pathological or diagnostic clinical specimen only Observation of public behaviour New treatment regime

Yes/No

- Is the information recorded in such a manner that subjects can be identified from information provided directly or through identifiers linked to the subjects?
- Does the research deal with sensitive aspects of the subject's behaviour; sexual behaviour, alcohol use or illegal conduct such as drug use?

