The project is an interdisciplinary and collaborative activity between three institutions that in the first instance focuses on the development of cholera monitoring and prediction in Mozambique. This is based on the consolidation of earlier research findings from a wide variety of sources including those based on Mozambique and Bangladesh through the recognized studies of those coordinating this proposal. The initial phase of the project focuses on testing the hypothesis that environmental influences on cholera ecology are similar in Mozambique to those in Bangladesh. This necessitates transfer of technology from Dhaka to Beira, for microbiological monitoring of cholera epidemic, and comparison with studies in Bangladesh. The collaboration requires capacity building in the Mozambique laboratories to streamline some existing procedures and to introduce new ways of monitoring *V. cholerae* from the environment and from the people who become cholera patients. The specific techniques for the microbiological analysis will include the following: culturing of diarrhoeagenic pathogens, monitoring of standard water quality indicators as well as physicochemical parameters of the water samples, further work on preserved samples, analysis of phytoplankton and zooplankton in selected water bodies, and the use of specific detection technologies such as fluorescent antibody technique and colony blot hybridization technique. In Bangladesh, we will carry out environmental surveillance of one pond and river in Matlab and the clinical data will be obtained from the hospital records of Matlab. This environmental and clinical surveillance will be carried out to have a comparative data of cholera endemic areas of Bangladesh and Mozambique.

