chamber, and will be incubated at 37°C for 30 ± 5 minutes protecting from light. Then the slides will be rinsed thoroughly with PBS protecting from light. Excess moisture will be absorbed using a blotting paper. A drop of fluorescent mounting medium will be added on the slide and covered with a 22 x50mm, No. 1 cover slip. For best results, the slides will be read immediately at a magnification of 1000 X with oil immersion. The slides will, however, be kept cool, in the dark, or will be kept humid to prevent drying.

Colony blot hybridization technique

Preparation of colony blots and hybridization will be carried out according to published procedures (Wright *et al.* 1992 and Maniates *et al.* 1982). Environmental water samples will be plated directly or upon appropriate 10 fold serial dilutions on non selective LB agar plates and incubated overnight at 37°C. Colonies will be transferred to a Whatman # 541 filter paper from the culture plates. The filters will be transferred with colony side up on to # 3 Whatman filters that are pre-soaked with denaturation solution (4 ml) for 10 minutes. The filter paper will be saturated with neutralizing solution (4 ml) for 3 min then the filter will be air dried and soaked in pre hybridization buffer at 42°C for 1 hour. Then hybridization will be carried out with DIG labelled ctx probe at 42°C for over night. Then the washing, blocking and signal detection will be carried out following the procedures provided by the manufacturers (Boehringer Mannheim, Japan).

Physicochemical parameters of water

Physicochemical measurement will be made at the time of collection at each sampling site. This will include water temperature, pH (Orion Portable pH Meter, Cat. No. 210 A, Orion Research, USA), salinity, total dissolved solids and conductivity (HACH Conductivity Meter, Cat. No. 51800-18, Sension™ 5, HACH Company, USA) and dissolved oxygen content (HACH Dissolved Oxygen Meter, Cat. No. 51850-18, Sension™ 6, HACH Company, USA). All these readings will be taken in the field using potable meters. The free CO₂, hardness and chloride will be measured in the laboratory following standard procedures (APHA, 1998). The number of hours of sunshine, total rainfall and the ambient temperature will be obtained from the Metrological Department of Bangladesh in Dhaka.

Clinical surveillance

Data on the incidence of cholera in Matlab, Bangladesh will be collected from the Matlab Hospital records of ICDDR,B.

Activities in Mozambique:

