Like Bangladesh, environmental samples will be collected from both lotic (open water, e.g., river, canal, sea etc.) and lentic (closed water, e.g., pond, lake, wells etc.) environment of Beira, Mozambique. Phytoplankton, zooplankton and water samples will be collected every two weeks interval. The samples will be transported to the CHAEM laboratory following standard procedures and processed following the same procedures as described in Bangladesh part. The isolation and identification of *V. cholerae* O1 and O139 will be carried out following enrichment technique as described in material and methods section in Bangladesh part. The VBNC *V. cholerae* O1 and O139 will also be detected using direct fluorescent antibody technique. All these methodologies will be set up in CHAEM laboratory by ICDDR,B as a part of technology transfer. Samples will be processed and preserved for detection of *V. cholerae* O1 and O139 by colony blot hybridization from the environmental samples. Preparation of colony blots will also be carried out in CHAEM and the dried blots will be sent to ICDDR,B for hybridization using DIG labelled probe.

The stool sample from the patients having watery diarrhoea from Infectious Diseases Hospital in Beira will be tested by dark field microscope as well as by using culture technique at CHAEM. The information about the patient will be taken from the record of Infectious Diseases Hospital.

The phytoplankton, zooplankton and chemical analysis will be carried out at CHAEM in Beira following the methods described in Bangladesh part.

Facilities Available

Describe the availability of physical facilities at the place where the study will be carried out. For clinical and laboratory-based studies, indicate the provision of hospital and other types of patient's care facilities and adequate laboratory support. Point out the laboratory facilities and major equipment that will be required for the study. For field studies, describe the field area including its size, population, and means of communications. (TYPE WITHIN THE PROVIDED SPACE).

The sampling sites will be selected at Matlab, a field study area of ICDDR, B located 70 km southeast of Dhaka in a low lying deltaic region. All the cholera patients from the sampling sites will be reported to the hospital for treatment. We will be able to know the time of cholera epidemic from the hospital records.

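### The ethics section declares that no human subject is involved, but the methods test stool from patients in Beira and take information from their hospital records

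*Protocol*

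**What the plan says.** The section Ethical Assurance for Protection of Human Rights asks for the justification for research in human subjects and for reasons if sick individuals are to be observed. It continues: "Indicate how subject's rights are protected and if there is any benefit or risk to each subject of the study". The whole answer is "No human subject is involved in this environmental study".

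The face sheet takes the same position. It reads "Consent Process (Check all that apply): Not Applicable" and "Determination of Risk: Does the Research Involve (Check all that apply): Not Applicable". The population groups, targeted population and sample size entries are also marked not applicable.

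The methods describe work with patients. The opening of the Methods section says that new ways of monitoring *V. cholerae* will be introduced "from the environment and from the people who become cholera patients". Under Activities in Mozambique the protocol states "The stool sample from the patients having watery diarrhoea from Infectious Diseases Hospital in Beira will be tested by dark field microscope", with culture at the CHAEM laboratory as well. The next sentence is "The information about the patient will be taken from the record of Infectious Diseases Hospital".

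For Bangladesh, the Clinical surveillance section says "Data on the incidence of cholera in Matlab, Bangladesh will be collected from the Matlab Hospital records of ICDDR,B".

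**The concern.** The declaration and the methods cannot both stand. Testing patients' stool and taking information about those patients from a hospital file, for a research project, is not an environmental study without human subjects. This is more than an omitted detail: the declaration itself is what makes consent and risk appear not to apply, so nothing further is said about either.

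At stake is the protection of the Beira patients. A committee that reads the ethics section and face sheet is told that there is nothing to examine. The questions it would otherwise ask then go unanswered: whether the stool is leftover diagnostic material or collected for the study, which record fields are taken, whether they are coded, and who holds them. The data are meant for research use. Under Collaborative Arrangements, data from both countries are to be combined for publication, and one collaborator is to use data from the project for a doctoral thesis. Consent and confidentiality are hard to repair once specimens and records have been taken.

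**Working it through.** No figure is at issue, so the check is a comparison of text.

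| Place in the protocol | Position on human subjects |
|---|---|
| Ethical Assurance section | None involved; no other text |
| Face sheet, consent process | Not applicable |
| Face sheet, determination of risk | Not applicable |
| Methods, opening paragraph | Monitoring extends to cholera patients |
| Activities in Mozambique | Patients' stool tested by microscopy and culture; patient information taken from hospital records |
| Clinical surveillance (Matlab) | Cholera incidence data from hospital records; no specimens described |

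1. *Are the conflicting statements both current text?* Yes. The ethics section, the face sheet and the methods are all parts of the protocol itself. None is a record of superseded wording.

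2. *Could lost checkbox marks explain the face sheet?* No. The words for not applicable are typed beside the headings. The risk list even offers a fitting option, for research that uses only pathological or diagnostic clinical specimens, but the heading rules out the whole list.

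3. *Does the ethics form ask about this situation?* Yes. Its prompt asks specifically about observations on sick individuals and about protection of subjects' rights. The answer addresses neither, because it denies that there are any subjects.

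4. *Is the Beira patient work incidental?* No. The Methods overview makes patient monitoring part of the project. The Background says that dark field microscopy has never been tried on clinical samples in Beira and will be introduced, so the project brings in the test.

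5. *Does any other available text supply the protection?* None states consent, a waiver, coding of data or confidentiality for the Beira patients. The Research Review Committee's memorandum lists nine points, a to i. None concerns human subjects or consent.

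6. *Does Matlab show the same conflict?* Only weakly. Its text speaks of incidence data, and the Facilities section uses the hospital records to learn when epidemics occur. Counts of that kind do not plainly contradict the declaration, so the finding rests on Beira.

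**The case against.** The best defence is that the stool testing is routine diagnosis. The Background says that Beira patients are already diagnosed now and then by plating stool or rectal swabs, and that dark field microscopy will go into a hospital's clinical pathology laboratory. The methods describe no extra specimen, patient contact or intervention. The hospital is named differently in the Background and in Activities in Mozambique, so this does not settle the matter, but it makes an exemption or waiver plausible and suggests that the risk to patients is low. That much stands. It does not make the declaration true: a waiver has to be stated and justified, the protocol does neither, and the argument does not cover the information taken from records.

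Three stronger readings are tempting, and the documents do not support them.

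- *The records are identifiable.* The protocol speaks only of information about the patient. It names no identifiers and no linkage. The face-sheet question on identifiability appears without a visible answer. Identifiability is unaddressed, not established.
- *No ethical review or consent exists.* Consent pages were removed from the text available, and the appendix checklist has items for consent forms and ethical assurance. The typed entry on the face sheet makes a hidden consent form unlikely, but only the absence of a provision in the available text can be asserted. The Research Review Committee did consider the protocol; its memorandum neither proves nor disproves ethical clearance.
- *The Mozambique half of the comparison would be lost.* The protocol nowhere says that the hospital series is the only source of Beira case data. The Background already draws on other Mozambican cholera data, including a published source on Beira and a correlation of cholera with rainfall, and the Ministry of Health is a collaborator. The Data Analysis section names no model that uses patient-level stool or record data.

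**Conclusion.** The point holds as a contradiction within the protocol. The ethics declaration is wrong as written, two face-sheet entries repeat the error, and the available text states no consent, waiver or confidentiality provision for the Beira surveillance component. It should be corrected before any patient specimen or record is used.

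The conflict reaches every Beira patient whose stool is tested or whose record is consulted. The protocol does not say how many that is, and marks sample size as not applicable. No sampling scheme, endpoint or analysis changes as a result. The component is surveillance, not a trial arm.

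The conclusion assumes only that testing patients' stool and taking patient information for a research project counts as involving human subjects, which the form's own prompts and risk options imply. It does not depend on the records being identifiable, on review having been absent, or on any loss of data.

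**What to change.** Reconcile the face sheet, Activities in Mozambique and the Ethical Assurance section.

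- Replace the declaration with a statement that the study tests stool from patients with watery diarrhoea in Beira and uses information from their hospital records, and that it uses cholera incidence data from Matlab Hospital records.
- Correct the face-sheet entries on consent process and determination of risk, and the other not-applicable entries that follow from the same declaration.
- Submit the component for ethical review, with either a consent procedure or a justified waiver. If the stool is leftover diagnostic material, say so, since that may support a waiver.
- Limit record extraction to the coded data needed for the case series, and state how confidentiality is kept.

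The cost is corrected wording and an ethics submission. No additional sampling or laboratory work is needed.
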